#### 1 Introduction to RAP documentation

### 1.1 Scope

The RAP documents contain detailed information to aid the production of Statistics & Programming input into the Clinical Study Report (CSR) for trial "CVAY736X2201".

Module 3 (M3) provides the description of the statistical methodology used to analyze the data, Module 7 (M7) details the presentation of the data, including shells of summary tables, figures and listings, and Module 8 (M8) contains programming specifications e.g. for derived variables and derived datasets, to support the creation of CSR outputs.

### 1.2 Changes to RAP documentation (M3)

Refer to corresponding guidances and Translational Sciences (TSc) RAP Addendum template for detailed information on the requirements of documenting changes to RAP documentation.

For the statistical methodology (M3), any major changes occurring before database lock to the statistical methodology should be reflected in the RAP M3 documentation via version control (new document version to be approved by the trial team as the original module.

Major changes include, but are not limited to, changes in protocol that affect study design and statistical methodology.

Minor changes to the RAP M3 documentation can be captured e.g. by a study note to file / note in RAP Addendum or within the CSR itself. Minor changes include, but are not limited to, change in statistical model. Corrections of typographical errors or modification of spelling (from English to American, for example) do not need to be incorporated into the RAP M3 documentation.

## 2 Study objectives and design

### 2.1 Study objectives

#### **Primary Objectives**

- To compare the effect of a single i.v. dose VAY736 versus placebo on the clinical disease activity of primary Sjögren's syndrome patients as measured by the change of a modified EULAR Sjögren's Syndrome Disease Activity Index (ESSDAI) between base line and Week 12.
- To assess the safety and tolerability of a single i.v. dose VAY736 in patients with primary Sjögren's syndrome as measured by adverse events (AEs).

### **Secondary Objectives**

- To evaluate the effect of a single i.v. dose VAY736 versus placebo on self-reported outcomes in pSS patients at 12 weeks compared to baseline as measured by the EULAR Sjögren's Syndrome Patient Reported Intensity (ESSPRI), the Short Form (36) Health Survey (SF-36) and the Multidimensional Fatigue Inventory (MFI) Questionnaire.
- To determine the changes in the physician global assessment of the patient's overall disease activity between baseline and Week 12 as recorded by a visual analog scale (VAS)
- To determine the changes in the patients global assessment of their disease activity between baseline and Week 12 as recorded by a VAS
- To determine the pharmacokinetics following a single dose i.v. VAY736 in pSS patients

#### **Exploratory Objectives**

- High resolution ultrasound of parotid salivary glands as measured by the following parameters:
  - Parotid thickness and staging
  - Parotid blood flow with contrast agent (optional)

    Corporate Confidential Information

- Salivary gland function using the salivary flow (unstimulated and stimulated)

  Corporate Confidential Information
- Lacrimal gland function using the Ocular Staining Score
- Serum evidence of B cell hyperactivity, Corporate Confidential Information
- To assess the immunogenicity following a single i.v. dose of VAY736 in pSS patients
- To measure the effect of a single i.v. dose VAY736 on leukocyte subsets,

Corporate Confidential Information

### 2.2 Study design and treatment

This is a double-blind, randomized, placebo-controlled, parallel-group, non-confirmatory study to assess the safety, tolerability, pharmacokinetics, immunogenicity, pharmacodynamics and clinical efficacy of VAY736 administered intravenously as a single dose in pSS patients. The patients will be enrolled in 2 sequential cohorts:

- 3 mg/kg cohort (Cohort 1): 6 patients randomized to receive a single dose of VAY736 at a starting dose of 3.0 mg/kg or placebo at a 2:1 ratio; approximately 4 patients in this cohort will receive a 3.0 mg/kg dose of VAY736 and approximately 2 patients will receive placebo.
- 10 mg/kg cohort (Cohort 2): 20 patients randomized to receive a single dose of VAY736 at a dose of 10.0 mg/kg or 3.0 mg/kg or placebo at a 6:1:3 ratio, respectively. Around 12 patients will receive 10 mg/kg of VAY736 in this cohort and around 6 will receive placebo. Approximately 2 patients will receive 3.0 mg/kg in this cohort to maintain a level of blinding regarding the dose received.

Between Cohort 1 and Cohort 2 recruitment will be paused and a safety review will be conducted by the VAY736 project team and the principle investigators.

The single doses of 3 - 10 mg/kg are based on the two highest doses safely administered in Part 1 of the SAD phase I study recently completed in RA patients. This study will enroll around 26 patients with primary Sjögren's syndrome. At least 24 subjects are expected to complete the study.

Subjects that are prematurely withdrawn from the study for reasons other than safety will be replaced on a case by case basis. Data from the withdrawn patients will still be used in the primary analysis as much as possible but the sponsor will use replacement patients to obtain complete data on at least 24 patients.

[figure not shown]
At Week 24 the blinding was broken to confirm treatment allocation. Investigators will follow the guidance below:

[figure not shown]
- If a patient received VAY736 and their B cell recovery was demonstrated at Week 24, then patients should have returned for their End of Study visit approximately 4 weeks later.
- Those patients who did not meet the criteria for B cell recovery at Week 24, will return to the site every 8 weeks until Week 52, then after Week 52, every 24 weeks until 2 years post dose (Week 100) and afterwards every 48 weeks, until B cell recovery is demonstrated and the End of Study visit may be scheduled.
- If a patient received placebo, at Week 24 they were offered the option of receiving open-label VAY736 (10 mg/kg) in a separate treatment arm.
  - Patients that consented to open-label VAY736 treatment would have restarted the study at Day 1 (within 4 weeks [+ 2 week window] of Week 24 visit);
  - o Patients that did not consent to receive open-label VAY736 treatment would have returned to the site for End of Study visit as per Assessment schedule.

Patients will not be informed of their treatment allocation until after all of the assessments scheduled for Week 24 have been completed.

A study design schematic is provided in Figure 2-1.

Figure 2-1 Study Design Schematic

Key: Placebo patients may enter into open-label VAY736 treatment and restart the study at Day 1; U unblinding at week 24

An interim analysis is planned after all patients have completed the week 12 visit in order to assess the effect of VAY736 on the primary endpoint.

## 3 First interpretable results (FIR)

First interpretable results (FIR) will be provided for this trial.

The study FIR template can be found in CREDI in the study RAP folder [file name]

The template shows the analysis / results to be presented in the FIR. Study outputs required to be created at the time of the FIR will be marked as "Key" in the M9.1 Tracking sheet output list.

## 4 Interim analyses

Prior to this amended RAP two interim analyses have been performed, firstly when 25 and secondly when all 27 subjects had completed the Week 12 visit in order to assess the effect of VAY736 on the primary endpoints. For these subjects the efficacy endpoints (along with relevant safety data) were examined as a preliminary evaluation of therapeutic effects.

In addition, an interim safety review was performed between Cohort 1 and Cohort 2.

Additional interim analyses may be conducted to support decision making concerning the current clinical study.

#### 4.1 Interim and Second CSRs

An interim CSR will be produced after all patients have completed up to Week 52 assessments or have completed the study before Week 52. Efficacy data up to each patients week 52 visit will be summarized in this interim CSR(see below for more details regarding the figures), while listings will have all data up to the DB freeze. All safety data will be listed and summarized up to the interim CSR freeze date. At the end of the study after all patients have had B cell recovery a second CSR will be produced describing the data from Week 52 onwards and including all end of study assessments.

The following rules will be used for the presentation of the data for the Week-52 interim CSR,

- 1) For the majority of PD summary figures (such as boxplots etc.), only data up to week 24 will be included. The exception includes B cell count data visualization which will show all the data.
- 2) For other PD visualizations such as overlaid individual plots, they will include all available PD data up to week 52.
- 3) For AEs and conmeds, the summaries where applicable will be done for the double-blinded period and open-label period separately.
- 4) For summary tables for PD/safety lab/VS/ECG the PD tables end at Week 52 visits; safety data may include data beyond.
- 5) For all outputs which include "uncleaned" data, a footnote will be added "All data up to 05Oct2016 (the last Week 52 visit) has been cleaned and data afterwards hasn't been fully cleaned yet".

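### By-visit B cell summaries after Week 24 over-represent VAY736 patients who have not yet recovered, and the time-to-event summary does not say how to handle those still depleted at the Week 52 report

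*SAP*

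**What the plan says.** Section 2.2 makes follow-up after Week 24 depend on the B cell result. For a patient on VAY736, if "their B cell recovery was demonstrated at Week 24, then patients should have returned for their End of Study visit", that visit falls about 4 weeks later. A patient not recovered at Week 24 comes back every 8 weeks to Week 52 and at longer intervals after that, until recovery is shown. A placebo patient either takes open-label VAY736 in a separate arm with the clock reset to Day 1, or has an End of Study visit.

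Section 4.1 sets the reporting windows for the Week 52 interim CSR. On efficacy: "Efficacy data up to each patients week 52 visit will be summarized in this interim CSR". Rule 1 stops most PD summary figures at Week 24, but for B cells: "The exception includes B cell count data visualization which will show all the data". Rule 2 takes individual overlay plots to Week 52, and rule 4 takes PD tables to Week 52.

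Section 7.4 plans a by-treatment summary of time-to-B-cell-event endpoints. It rules out Kaplan-Meier estimates and log-rank tests because placebo patients showed no depletion. Section 7.1 schedules ESSDAI at baseline and Weeks 6, 12 and 24 only.

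**The concern.** B cell count determines who is still attending, and it is also the variable shown without a Week 24 cut-off. Once a patient has recovered and left, that patient's normal counts drop out of later visit rows and boxplots. The remaining group is weighted towards slow recoverers, with no concurrent randomized placebo group beside it. A reader who takes duration of depletion from these displays will read it as longer than it was among all dosed patients.

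The display that should answer the duration question, the time-to-event summary, has no stated method for patients still depleted at the interim cut. Section 4.1 expects such patients, since it plans a second CSR once everyone has recovered. If durations were summarized only in patients with an observed recovery, the longest ones would be left out.

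**Working it through.** **1. Number of dosed patients.** From Section 2.2:
- First cohort, "6 patients randomized to receive a single dose of VAY736 at a starting dose of 3.0 mg/kg or placebo at a 2:1 ratio": 6 × 2/3 = 4 on VAY736 and 6 × 1/3 = 2 on placebo.
- Second cohort, "20 patients randomized to receive a single dose of VAY736 at a dose of 10.0 mg/kg or 3.0 mg/kg or placebo at a 6:1:3 ratio": 20 × 6/10 = 12, 20 × 1/10 = 2 and 20 × 3/10 = 6.
- Total: 4 + 12 + 2 = 18 on VAY736 (6 at 3 mg/kg, 12 at 10 mg/kg) and 2 + 6 = 8 on placebo, 26 in all.

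This agrees with the stated total: "This study will enroll around 26 patients with primary Sjögren's syndrome". Section 4 counts one more patient ("secondly when all 27 subjects had completed the Week 12 visit") without giving the arm, so 18 is used below.

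**2. Direction.** Let S(t) be the share of all dosed VAY736 patients still depleted at week t. A patient attends visit k if not recovered at visit k−1. Among attendees, the share still depleted is

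S(t_k) / S(t_{k−1}),

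which is never below S(t_k), because S(t_{k−1}) ≤ 1. The two are equal only if nobody had recovered by the previous visit or nobody remains depleted. This takes recovery as a one-time event, with no other dropout and no End of Study values counted in a scheduled visit row.

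**3. Illustrative size.** The SAP gives no recovery times. Assume log-normal times with median m and log-SD s, so S(t) = 1 − Φ(ln(t/m)/s), and visits at Weeks 24, 32, 40, 48 and 52.

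Worked case, m = 40, s = 0.5, Week 52:
- S(52) = 1 − Φ(0.262/0.5) = 0.300
- S(48) = 1 − Φ(0.182/0.5) = 0.358
- Share depleted among those seen: 0.300/0.358 = 84%, against 30% of all dosed
- Expected number seen: 18 × 0.358 = 6.4

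Ranges over s = 0.3 and s = 0.5:

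| Median (weeks) | Week 40: all dosed | Week 40: those seen | n seen | Week 52: all dosed | Week 52: those seen | n seen |
|---|---|---|---|---|---|---|
| 24 | 4–15% | 26–54% | 3.0–5.1 | 0–6% | 48–74% | 0.2–1.5 |
| 32 | 23–33% | 46–66% | 9.0 | 5–17% | 60–79% | 1.6–3.8 |
| 40 | 50% | 65–74% | 12.1–13.9 | 19–30% | 70–84% | 4.9–6.4 |
| 52 | 70–81% | 84–85% | 15.0–17.0 | 50% | 83–89% | 10.1–10.9 |

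(Percentages are the share still depleted.)

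**4. Sensitivity of the size.** The figures here are the share recovered at Week 52, with s = 0.5 unless stated.
- *Visit grid.* Steps of 8 weeks from Week 24 reach 48 and then 56, so the exact visits before Week 52 are an assumption. For m = 36, 77% of all dosed have recovered, against 18% of those seen; with visits at Weeks 28, 36, 44 and 52 the 18% becomes 33%. For m = 48, it is 56% against 13%, or 23% on the second grid.
- *End of Study visits.* If a patient found recovered at Week 48 returns 4 weeks later and is tabulated at Week 52, the share recovered among those seen is 1 − S(52)/S(40). The 18% becomes about 45% and the 13% about 32%. The SAP does not say where these visits are tabulated.
- *Slow recovery.* For m = 78, s = 0.3, it is 9% of all dosed against 4% of those seen. At Week 40 both are about 1%.

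**The case against.** The strongest reply is that these are descriptive displays in a non-confirmatory study, that the Week 12 primary comparison is untouched, and that duration is covered elsewhere. Section 7.4 has the time-to-event summary. Section 6 plans PK/PD modelling of the extent and duration of depletion, with individual B cell counts overlaid on concentrations. Section 4.1 gives individual overlays and full listings, and the second CSR comes after all patients have recovered. Most of this stands, and it limits the harm. It does not close the gap at the interim CSR: the absence of depletion on placebo is a reason to drop a comparison with placebo, not a reason to omit a per-dose estimate that handles VAY736 patients still depleted at the cut.

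A reader might also infer more than the SAP supports:
- *Later summaries contain only unrecovered patients and cannot show recovery.* Not so. A patient is followed until recovery is shown and is counted at that visit. End of Study values may also contribute, and the open-label arm has its own visits.
- *Durability of efficacy is misstated too.* Not shown. ESSDAI ends at Week 24, the two global assessment endpoints are defined to Week 12 (Section 7.3), and the SAP schedules no efficacy measure after Week 24. For PD variables other than B cells the group is selected, but the direction of any distortion cannot be derived.
- *The missing placebo group is an analysis error.* It follows from the design.
- *The tables should stop at Week 24.* That would discard planned data when labelling deals with the misreading.

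**Conclusion.** The point holds for by-visit B cell figures and tables after Week 24. The exit rule selects on the variable displayed, so they overstate persistence relative to all dosed patients. The direction rests on recovery being a one-time event that ends scheduled follow-up. The size is not established: the illustrations run from near zero (slow recovery, early visits) to a difference of more than 50 percentage points at Week 52 (for example 19–30% against 70–84%), and they depend on assumed recovery times, visit weeks and handling of End of Study visits. The time-to-event summary is only a partial safeguard while the handling of still-depleted patients is unstated. This should be corrected before the interim CSR, but it does not bear on the primary analysis.

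**What to change.** In Section 7.4, report time to B cell recovery separately for each VAY736 dose, with all dosed patients in the denominator. Use a Kaplan-Meier or interval-censored estimate with patients still depleted at the data cut censored; the interval-censored form respects the fact that recovery is detected only at visits. A table of the cumulative number recovered out of all dosed is a simpler alternative. State that conclusions on duration of depletion rest on this output. The placebo comparison and log-rank test can stay out.

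In Section 4.1, keep the later B cell figures and PD tables, show n at each visit, and label VAY736 results after Week 24 as coming from patients still in follow-up because not yet recovered at the previous visit.

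The cost is SAP wording, footnotes in the shells and one extra descriptive output per dose. With about 6 and 12 patients per dose, the intervals will be wide.

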## 5 Statistical methods: Analysis sets

For subjects for which the actual treatment received does not match the randomized treatment the treatment actually received will be used for the analysis.

All subjects that received study drug and with no protocol deviations with relevant impact on safety will be included in the safety analysis set.

The PK analysis set will include all subjects with at least one available valid (i.e. not flagged for exclusion) PK concentration measurement, who received any study drug and experienced no protocol deviations with relevant impact on PK data.

The PD analysis set will include all subjects with any available PD data, who received any study drug and experienced no protocol deviations with relevant impact on PD data.

The analysis sets and protocol deviation codes are related as follows:

Table 5-1 Protocol deviation severity codes and analysis sets

Protoc	col deviation severity code	Safety analysis set	PK analysis set	PD analysis set
Code	Text			
5	Exclude subject from all safety analysis	-	-	-
8	Exclude from all analyses	-	-	-
20	Exclude subject from PK analysis set	+	-	+
22	Exclude subject from PD analysis set	+	+	-
23	Exclude subject from PK and PD analysis set	+	-	-
49	Report relevant protocol deviation – include subject in all analysis sets	+	+	+

+ = include in analysis set, - = exclude from analysis set, NA = not applicable

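### The safety analysis set can leave out dosed patients because of a safety-relevant protocol deviation, and so may remove them from the adverse event percentages for a primary objective

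*SAP*

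**What the plan says.** SAP section 5 sets two conditions for the safety set: "All subjects that received study drug and with no protocol deviations with relevant impact on safety will be included in the safety analysis set". The same section says that subjects are analysed under the treatment they actually received.

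Table 5-1 links deviation codes to the sets. Two codes carry a minus under Safety: code 5, "Exclude subject from all safety analysis", and code 8, "Exclude from all analyses". Both also carry a minus under PK and PD. Two other codes keep the subject in the safety set: code 23, "Exclude subject from PK and PD analysis set", and code 49, which reports the deviation and says "include subject in all analysis sets".

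The text gives the PK and PD sets their own criteria. The PK set takes subjects "who received any study drug and experienced no protocol deviations with relevant impact on PK data" who have a valid concentration. The PD set takes dosed subjects with PD data who "experienced no protocol deviations with relevant impact on PD data". Neither definition requires membership of the safety set.

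The second primary objective in section 2.1 begins "To assess the safety and tolerability of a single i.v. dose VAY736" and is measured by AEs. Section 8 reports AEs as counts and percentages of subjects per treatment, together with a by-subject display of all AE information. It does not say which analysis set the counts use.

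**The concern.** A safety set normally holds everyone who was exposed, because the question is what happened to the people who received the product. Here a dosed patient can be left out, and the trigger is that the deviation mattered for safety. That is a patient whose events a reader would particularly want to see counted. AEs carry a primary objective and the arms are small, so the absence of one patient would visibly move a percentage. It could also make an event that occurred only once disappear from the summary table.

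**Working it through.** **1. What the clause can do.** The safety set is (dosed) and (no safety-relevant deviation). An undosed subject fails the first condition whatever the second says. Those removed by the second condition alone are therefore exactly the dosed subjects with a safety-relevant deviation. The clause has no effect on anyone else.

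**2. Planned arm sizes (section 2.2).**
- Cohort 1, 6 patients at 2:1: 6 × 2/3 = 4 on 3 mg/kg and 6 × 1/3 = 2 on placebo.
- Cohort 2, 20 patients at 6:1:3: 20 × 6/10 = 12 on 10 mg/kg, 20 × 1/10 = 2 on 3 mg/kg and 20 × 3/10 = 6 on placebo.
- Totals: 12 on 10 mg/kg, 4 + 2 = 6 on 3 mg/kg and 2 + 6 = 8 on placebo. The sum is 26, which reproduces the planned enrolment.

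These denominators apply to the double-blind period only. Section 4.1 summarises AEs separately for the open-label period, in which placebo patients may receive VAY736.

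**3. Weight of one patient (1/n).** Section 4 reports 27 subjects at the second interim analysis but not their split, so the last column adds the extra subject to each arm in turn.

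| Arm | Planned n | 1/n | 1/(n+1) |
|---|---|---|---|
| 10 mg/kg | 12 | 8.3% | 7.7% |
| 3 mg/kg | 6 | 16.7% | 14.3% |
| Placebo | 8 | 12.5% | 11.1% |

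**4. Effect on an AE percentage when one patient is excluded.** With x patients having the event, x/n becomes (x − 1)/(n − 1) if the excluded patient had it, and x/(n − 1) if not. The values of x and the single exclusion are assumptions for illustration.

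| Arm | x = 1, excluded patient had it | x = 2, all dosed | x = 2, excluded patient had it | x = 2, excluded patient did not |
|---|---|---|---|---|
| 10 mg/kg | 1/12 = 8.3% to 0/11 = 0% | 2/12 = 16.7% | 1/11 = 9.1% | 2/11 = 18.2% |
| 3 mg/kg | 1/6 = 16.7% to 0/5 = 0% | 2/6 = 33.3% | 1/5 = 20.0% | 2/5 = 40.0% |
| Placebo | 1/8 = 12.5% to 0/7 = 0% | 2/8 = 25.0% | 1/7 = 14.3% | 2/7 = 28.6% |

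The shift can go in either direction.

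**5. Table 5-1, label against row (Safety, PK, PD).**

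| Code | Sets named in the label | Row implied by the label | Row printed |
|---|---|---|---|
| 5 | Safety | −, +, + | −, −, − |
| 8 | All | −, −, − | −, −, − |
| 20 | PK | +, −, + | +, −, + |
| 22 | PD | +, +, − | +, +, − |
| 23 | PK and PD | +, −, − | +, −, − |
| 49 | None | +, +, + | +, +, + |

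Five of the six rows agree with their labels. Code 5 does not, and its row duplicates that of code 8.

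**The case against.** **The AE tables may not use this set.** Section 8 names no set, displays all AE information by subject, and section 4.1 says that all safety data are to be listed and summarised up to the freeze date. This stands in part. Use of the safety set is an inference from its name and from the code 5 label, which covers every safety analysis. The section 4.1 sentence is most naturally a data cut-off. If it were instead read as a promise to summarise every patient, it would conflict with section 5, which would still need correcting. The by-subject display keeps the events visible but does not return the patient to the counts and percentages.

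**No case is shown.** This stands. The study is small and non-confirmatory, and the SAP reports no subject with code 5 or 8. A reader might infer that exposed patients were in fact dropped and the AE rates distorted. The document does not support that; it shows only that the rule permits it.

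**The code 5 row may be deliberate.** A reader might infer that this row contradicts the PK and PD definitions. That goes too far. Relevant impact is not defined, and a deviation serious enough to bar a subject from safety analysis could also be judged relevant to PK and PD, in which case row and text agree. What remains is that the label names less than the row does and that the code is redundant beside code 8. Nor can it be said that code 5 removes patients from the primary ESSDAI analysis: that endpoint sits under the PD methods, but section 7.1 names no analysis set for it.

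**Code 8 may serve a purpose.** The SAP does not say what it is for, so the fix should allow relabelling as well as deletion.

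**Conclusion.** The safety set definition is wrong as written and should be changed. Its deviation clause, applied through codes 5 and 8, can act only on exposed patients, and nothing elsewhere in the SAP overrides it. One excluded patient would be 8.3%, 16.7% or 12.5% of the planned 10 mg/kg, 3 mg/kg or placebo arm in the double-blind period.

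This rests on three assumptions: that the AE counts use the safety set, that the arms are close to their planned size, and that at least one subject is coded 5 or 8. If no subject is, there is no numerical effect. The mismatch between the code 5 label and its row is a minor inconsistency with no size attached.

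**What to change.** - Define the safety set as all subjects who received any study drug (VAY736 or placebo), analysed by treatment received, with no exclusion for protocol deviations.
- Delete code 5. The other five rows already match their labels, so no PK or PD column then needs correcting.
- Delete code 8, or relabel it so that it does not remove dosed subjects from the safety set. Code 23 already covers exclusion from PK and PD with safety kept, and code 49 covers reporting a deviation with the subject kept in every set.
- Name the safety set as the basis of the AE counts and percentages in section 8.
- List deviations alongside the safety data, so that a reader can judge their bearing on any event.

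The cost is one sentence and two table rows in section 5, plus a short clarification in section 8. No new data are needed.

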## 7 Statistical methods for Pharmacodynamic (PD) parameters

### 7.1 Primary parameter

The primary aim of this study is to evaluate the effect of a single i.v. dose VAY736 on the clinical disease activity of primary Sjögren's syndrome patients as measured by the ESSDAI at Week 12 compared to baseline. The statistical analysis model will include data on the ESSDAI from all timepoints at which it was recorded (baseline, Weeks 6, 12 and 24) but the primary comparison is made for Week 12.

The ESSDAI is an established disease outcome measure for Sjögren's syndrome that will be applied to the study patients at baseline and again at Weeks 6, 12 and 24. The instrument contains 12 organ-specific domains contributing to disease activity. For each domain, features of disease activity are scored in 3 or 4 levels according to their severity. These scores are then summed across the 12 domains in a weighted manner to provide the total score.

It is assumed that the ESSDAI will follow an approximate normal distribution. If, on blinded review of the data, this assumption appears to not be met, alternative statistical methods may be applied, e.g. data may be log transformed with changes from baseline in the log transformed data being analyzed.

A positive sign of therapeutic effects will be considered to be a difference of at least 5 points in the change from baseline between VAY736 and placebo with a moderate level of evidence. Additionally there should be a high level of evidence that is a difference between VAY736 and placebo. The two active doses will be pooled for the primary efficacy analysis (unless there is evidence of inferiority of the 3 mg/kg dose to the 10 mg/kg dose). These criteria will be evaluated by calculating Bayesian posterior probabilities as follows:

```
Pr (\theta_{VAY736,12w}-\theta_{placebo,12w}>0 \mid data) > 90\% and Pr (\theta_{VAY736,12w}-\theta_{placebo,12w}>5 \mid data) > 50\% where \theta means change from baseline in ESSDAI at 12 weeks.
```

It is assumed that  $Y_{ijt}$ , the observed change from baseline in ESSDAI for subject i receiving treatment j (VAY736 or placebo) at time t, follows a normal distribution  $N(\theta_{jt}, \sigma^2)$ , It is further assumed that  $\theta_{jt}$  follows a standard non-informative prior Normal distribution,  $p(\theta_{jt}, \sigma^2) = 1/\sigma^2$ .

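### The primary efficacy comparison is planned as treated, in a set that drops whole patients for protocol deviations, with no as-randomised analysis beside it

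*SAP*

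**What the plan says.** SAP section 5 opens with a rule for patients whose treatment differs from their allocation: "the treatment actually received will be used for the analysis". The rule is not limited to safety or PK.

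The section then defines three analysis sets, each with a deviation exclusion:
- Safety: "All subjects that received study drug and with no protocol deviations with relevant impact on safety will be included in the safety analysis set".
- PK: at least one valid concentration, any study drug, and no deviation relevant to PK.
- PD: any PD data, for dosed patients who "experienced no protocol deviations with relevant impact on PD data".

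In Table 5-1, code 22 reads "Exclude subject from PD analysis set". Codes 5, 8 and 23 also remove the whole patient from the PD set. Code 49 reports a relevant deviation but keeps the patient in every set.

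The primary ESSDAI analysis is section 7.1, under the heading "Statistical methods for Pharmacodynamic (PD) parameters". Section 7.1 names no analysis set. The supportive analyses in section 7.2 change the time model and explore dose; they change neither the patients nor the grouping. Section 7.3 reuses the primary model's factors for the secondary efficacy variables.

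**The concern.** The efficacy question is a randomised comparison of VAY736 with placebo, judged by a formal two-part rule. Randomisation protects that comparison only if patients stay in the group they were allocated to and are not removed because of events after allocation. The SAP allows both departures. The phrase relevant impact on PD data is not defined, and such a deviation can occur after randomisation and may be related to arm or outcome.

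An as-treated, deviation-restricted analysis is normal for PK and reasonable as a supportive efficacy analysis. Here it is the only efficacy analysis planned. With a placebo arm this small, one exclusion or one active/placebo swap could matter to a result near a criterion, and the planned outputs would not show it.

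**Working it through.** **1. Which set applies.** Section 7.1 does not name its set; the PD set is inferred from the heading. The point does not depend on that inference, because all three sets exclude for deviations and the as-treated rule covers every analysis.

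**2. Planned arm sizes (section 2.2).**
- Cohort 1, 6 patients at 2:1: 6 × 2/3 = 4 active, 6 × 1/3 = 2 placebo.
- Cohort 2, 20 patients at 6:1:3: 12 at 10 mg/kg, 2 at 3 mg/kg, 6 placebo.
- Total: 4 + 12 + 2 = 18 active and 2 + 6 = 8 placebo, 26 in all. This reproduces the SAP's planned figures.

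Section 4 reports 27 patients at the second interim analysis, without the split by arm. Eight is therefore a planned, approximate count.

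**3. Shift from one exclusion.** If seven placebo patients have mean m and the eighth has m + d, the mean of eight is m + d/8. Removing the eighth moves the raw placebo mean by d/8. The SAP gives no SD, so d is assumed.

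| Assumed d (points) | Shift d/8 (points) | Share of the 5-point criterion |
|---|---|---|
| 5 | 0.625 | 12.5% |
| 10 | 1.25 | 25% |
| 15 | 1.875 | 37.5% |

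Under the flat prior in section 7.1, a posterior probability above 50% of a difference over 5 points amounts, in a simple two-group setting, to a point estimate over 5. A shift of this size therefore acts directly on that criterion.

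**4. Loss of precision.** SE/SD = √(1/18 + 1/n), with n the number of placebo patients.
- n = 8: 0.425.
- n = 7: 0.445, up 4.8%.
- n = 6: 0.471, up 10.9%.

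Precision is the smaller issue; selection is the larger one.

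**5. Worst-case bound.** This simulation used 200,000 trials with no true effect, 18 versus 8 patients, normal Week 12 data only, the 1/σ² prior, and positive values meaning improvement. It compares the full set with a free option to drop the single best placebo responder.
- The chance that the probability of any benefit exceeds 90% rises from about 10% to about 21%.
- The chance of meeting both criteria rises as follows.

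| Assumed SD | All patients | Option to drop one |
|---|---|---|
| 4 | 0.2% | 0.8% |
| 6 | 2.5% | 7.1% |
| 8 | 6.8% | 15.7% |
| 10 | 9.4% | 19.8% |

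This bounds the vulnerability to one such exclusion in a simplified model. It does not estimate what happened in the trial.

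**The case against.** Several points on the other side stand.

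- **Timing of exclusions.** A reader might infer that exclusions were, or may be, decided with arm and outcome known. Section 2.2 describes unblinding at Week 24, and section 4 says: "Prior to this amended RAP two interim analyses have been performed". The SAP does not support that inference. It does not say when, by whom or under what blinding deviation codes are assigned, and the protocol may. Sections 7.1 and 7.2 give no such rule either: blinded review is mentioned in 7.1 only, for normality and the missing-at-random assumption. That is silence, not permission.
- **Broken randomisation.** A reader might conclude that randomisation has been lost. No excluded or mis-dosed patient is reported; the text supports only that preservation is not guaranteed.
- **Conflict with section 2.2.** That section says: "Data from the withdrawn patients will still be used in the primary analysis as much as possible". This concerns withdrawals, whereas section 5 concerns deviations. The two rules do not contradict each other.
- **Narrow reach of the as-treated rule.** Dosing is a single infusion, and open-label VAY736 for placebo patients comes only after Week 24, so a Week 12 mismatch needs a dosing error. With the active doses pooled, only an active/placebo swap changes a patient's group.
- **Not every deviation excludes.** Code 49 keeps a patient with a relevant deviation in all sets.
- **Size.** The values of d and SD are assumed, the estimate comes from a baseline-adjusted repeated-measures model rather than raw means, and a shift decides the outcome only if the result is already close to a criterion.
- **Purpose.** The study is described as non-confirmatory and looks for a positive sign of effect.
- **Late change.** Replacing the primary set now, after two looks at the endpoint, would itself be a change made with results known.

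These points limit the claim and shape the remedy. They do not supply the missing as-randomised analysis.

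**Conclusion.** The point holds as a stated analysis choice: efficacy is analysed as treated, every available set can drop whole patients for deviations, and nothing planned would show whether that changed the answer. The randomised comparison is not guaranteed to be preserved.

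One excluded placebo patient would move the raw placebo mean by 0.6 to 1.9 points, assuming 8 placebo patients and a difference of 5 to 15 points from the others. That is 12.5% to 37.5% of the 5-point criterion. The actual effect is unknown. If nobody was excluded from the PD set and no active/placebo swap occurred, the as-randomised and planned pooled comparisons would coincide on this point.

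The change should be made, because it is cheap and the SAP sets a formal success rule. The study's non-confirmatory purpose argues against ranking it higher.

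**What to change.** - State in section 7.1 which analysis set the planned ESSDAI analysis uses.
- Add an as-randomised analysis of the ESSDAI and the secondary efficacy endpoints. Include all randomised, dosed patients with a baseline value and whatever post-baseline data exist, regardless of deviation code, with no completeness requirement beyond what the model needs.
- Report it beside the PD-set, as-treated result. If the two differ, base the efficacy conclusion on the as-randomised analysis.
- Disclose that it was added after the two interim analyses; do not silently replace the existing set.
- Keep treatment received for safety and PK.
- List every patient excluded from the PD set by code 5, 8, 22 or 23, with the date of the decision and whether it was made blinded.

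The cost is SAP wording, a short listing and one extra model run per endpoint. The drawback is slight dilution of the estimate if an active/placebo mis-dosing did occur; the as-treated result beside it would show this. If no patient is affected, one sentence in the study report settles the point.
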